### Part 3 - Year 1 (cont.)

| Treatment Week  | Part 3 Week 1  | Part 3 Week 4 | Part 3 Week 8 | Part 3 Week 12 | Part 3 Week 16 | Part 3 Week 20 | Part 3 Week 24 | Part 3 Week 28 | Part 3 Week 32 | Part 3 Week 36 | Part 3 Week 40 | Part 3 Week 44 | Part 3 Week 48 | Part 3 Week 52 | Unscheduled | Prior to Start of Dopaminergic/Symptomatic PD Treatment (if occurring during Part 3) | Part 3 Early Termination (if occurring during Part 3) | Part 3 12 Week Treatment Free FUP  (at end of study or if treatment terminated early in Part 3) |
|---|----------------|---------------|---------------|----------------|----------------|----------------|----------------|----------------|----------------|----------------|----------------|----------------|----------------|----------------|-------------|--|---|--|
| Treatment Day   | Day 1          | Day 28        | Day 56        | Day 84         | Day 112        | Day 140        | Day 168        | Day 196        | Day 224        | Day 252        | Day 280        | Day 308        | Day 336        | Day 364        |             |  |   |  |
| Visit Window  |                | +/- 4 days    | +/- 4 days    | +/- 4 days     | +/- 4 days     | +/- 4 days     | +/- 4 days     | +/- 4 days     | +/- 4 days     | +/- 4 days     | +/- 4 days     | +/- 4 days     | +/- 4 days     | +/- 4 days     |             |  |   | +/- 7 days   |
| Dose Number   | 1              | 2             | 3             | 4              | 5              | 6              | 7              | 8              | 9              | 10             | 11             | 12             | 13             | 14             |             |  |   |  |
| Assessments   |                |               |               |                |                |                |                |                |                |                |                |                |                |                |             |  |   |  |
| Triplicate ECG-12 lead    | X              |               |               |                |                |                |                |                |                |                |                |                |                |                | X           | X  | X   | X  |
| Pre dose 12-Lead ECG  |                |               |               |                |                |                | X              |                |                |                |                |                |                | X              | X           |  |   |  |
| DaT-SPECT    |                |               |               |                |                |                |                |                |                |                |                |                |                |                |             |  | X                                        |  |
| MRI (safety & efficacy)    | X  |               |               |                |                |                |                |                |                |                |                |                |                |                | X           |  | X                                        |  |
| Hematology  | X  |               |               | X              |                |                | X              |                |                | X              |                |                |                | X              | X           | X  | X   | X  |
| Blood Chemistry and Lipids  | X  |               |               |                |                |                | X              |                |                |                |                |                |                | X              | X           | X  | X   | X  |
| Coagulation   | X  |               |               |                |                |                | X              |                |                |                |                |                |                | X              | X           | X  | X   | X  |
| TSH and T4  |                |               |               |                |                |                |                |                |                |                |                |                |                | X              | X           |  | X                                        |  |
| Urinalysis  | X  |               |               |                |                |                | X              |                |                |                |                |                |                | X              | X           | X  | X   | X  |
| Pregnancy Test   | X              | X             | X             | X              | X              | X              | X              | X              | X              | X              | X              | X              | X              | X              | X           | X  | X   | X  |
| Serum RO7046015 (PK sampling)                                        | X              |               |               |                |                |                | X              |                |                |                |                |                |                | X              | X           |  | X   | X  |
| Serum and plasma Biomarker   | X              |               |               |                |                |                | X              |                |                |                |                |                |                | X              | X           | X  | X   | X  |
| Serum Anti-RO7046015 Antibody                                        | X              |               |               |                |                |                | X              |                |                |                |                |                |                | X              | X           |  | X   | X  |
| Optional CSF via Lumbar Puncture (matching serum and plasma sample)  |                |               |               |                |                |                |                |                |                |                |                |                |                |                |             | X  | X                                        |  |

### Part 3 - Year 1 (cont.)

| Treatment Week  | Part 3 Week 1   | Part 3 Week 4 | Part 3 Week 8 | Part 3 Week 12 | Part 3 Week 16 | Part 3 Week 20 | Part 3 Week 24 | Part 3 Week 28 | Part 3 Week 32 | Part 3 Week 36 | Part 3 Week 40 | Part 3 Week 44 | Part 3 Week 48 | Part 3 Week 52 | Unscheduled | Prior to Start of Dopaminergic/Symptomatic PD Treatment (if occurring during Part 3) | Part 3 Early Termination  (if occurring during Part 3) | Part 3 12 Week Treatment Free FUP  (at end of study or if treatment terminated early in Part 3) |
|---|-----------------|---------------|---------------|----------------|----------------|----------------|----------------|----------------|----------------|----------------|----------------|----------------|----------------|----------------|-------------|--|---|--|
| Treatment Day   | Day 1           | Day 28        | Day 56        | Day 84         | Day 112        | Day 140        | Day 168        | Day 196        | Day 224        | Day 252        | Day 280        | Day 308        | Day 336        | Day 364        |             |  |   |  |
| Visit Window  |                 | +/- 4 days    | +/- 4 days    | +/- 4 days     | +/- 4 days     | +/- 4 days     | +/- 4 days     | +/- 4 days     | +/- 4 days     | +/- 4 days     | +/- 4 days     | +/- 4 days     | +/- 4 days     | +/- 4 days     |             |  |   | +/- 7 days   |
| Dose Number   | 1               | 2             | 3             | 4              | 5              | 6              | 7              | 8              | 9              | 10             | 11             | 12             | 13             | 14             |             |  |   |  |
| Assessments   |                 |               |               |                |                |                |                |                |                |                |                |                |                |                |             |  |   |  |
| PreMedication Loratadine 10mg PO, Acetaminophen 650 mg PO  |                 |               |               |                |                |                |                |                |                |                |                |                |                |                | X           |  |   |  |
| Administration of Study Medication                                      | X  | X             | X             | X              | X              | X              | X              | X              | X              | X              | X              | X              | X              | X              |             |  |   |  |
| Skin Biopsy   |                 |               |               |                |                |                |                |                |                |                |                |                |                |                |             | X   | X   |  |
| RBR - Optional Whole Blood RNA  |                 |               |               |                |                |                |                |                |                |                |                |                |                | X              |             | X  | X   | X  |
| RBR - Optional Whole Blood Plasma                                       |                 |               |               |                |                |                |                |                |                |                |                |                |                | X              |             | X  | X   | X  |
| Adverse Events  | X               | X             | X             | X              | X              | X              | X              | X              | X              | X              | X              | X              | X              | X              | X           | X  | X   | X  |
| Previous and Concomitant Treatments                                     | X               | X             | X             | X              | X              | X              | X              | X              | X              | X              | X              | X              | X              | X              | X           | X  | X   | X  |

### Part 3 - Year 1 (cont.)

- 1 The participants must meet the following criteria to enter the Part 3: Having completed Part 2 (i.e., completed Week 104 visit) and having completed the 12 week treatment free follow up visit.
- 2 Not needed for the participants who performed 12-week treatment free FUP visit less than 30 days from Part 3 Week 1 visit ago
- 3 Hoehn & Yahr staging will be assessed as part of the MDS-UPDRS Part III. MDS-UPDRS Part IV will be done for all participants on dopaminergic treatment. For all participants that have started dopaminergic treatment MDS-UPDRS Part III and Part IV will be assessed approximately 12 hours (e.g., overnight) after last dose of dopaminergic treatment. MDS-UPDRS Part III will then be repeated at least 1 hour after dopaminergic treatment along with MDS-UPDRS Part IV and Digital Biomarker assessments.
- 4 Vital signs (including semi-supine blood pressure, respiratory rate and pulse rate) have to be monitored pre-infusion, every 15 minutes until the end of infusion, and thereafter, every 30 minutes until the infusion line is removed. In order to assess for orthostatic hypotension, BP and pulse rate will be evaluated after 2 minutes of standing still (after the semi-supine measurement) at pre-dose and 1 hour after end of infusion. Note: any abnormal value in Vital Signs needs to be repeated for confirmation or intervention if needed.
- 5 Including weight
- 6 Abbreviated physical exam will include Head Ears Eyes Nose and Throat (HEENT), Heart & Lung exams and any complaints expressed by participant at visit
- 7 The PROs (patient reported outcome) are scheduled at regular intervals and administered on the digital biomarker smartphone. The PROs will typically be completed remotely since the scheduled days will often fall between clinic visit days.
- 8 In Clinic Digital Biomarker Assessments only include the Full Active Test.
- 9 On Part 3 Week 1 ECG will be obtained pre-dose and at end of study drug infusion. For the Part 3 early termination/Part 3 FUP the ECG timing should be early in the visit to approximate the pre-dose measurements. For all the designated visits, ECGs (12-lead ) will be performed in triplicate, 1-2 minutes apart within 5 minutes.
- 10 MRIs should be performed with a time window of +/- 14 days from the study visit. DaT-SPECT should be performed within -14/-5 days if done prior to the clinic visit or within +14 days if done after the visit clinic. Refer to protocol Section 4.6.1.9 for procedure to follow in preparation of scans. In case participant takes dopaminergic treatment, MRI should be performed in a practically defined off state (no dopaminergic medication taken at the day of evaluation).
- 11 Urine pregnancy test for female participants (based on participant age/menopausal status) performed prior to dosing and all DaT-SPECT Scans.
- 12 Serum RO7046015 (PK sampling) will be collected just prior to dosing and at the end of the infusion; serum and plasma biomarkers samples will be collected just prior to dosing . At Part 3 early termination and Part 3 FUP: Serum RO7046015 (PK sampling) and serum & plasma biomarkers sampling will be collected anytime (all time points of collection to be recorded in CRF).
- 13 On dosing days Serum anti-RO7046015 antibody samples will be collected prior to dosing.
- 14 For consented participants only. The ideal collection time to perform Lumbar Puncture (LP) is between 48-72 hours after early termination. LP should be performed in the morning (between 8:00 and 12:00 hours) to minimize potential diurnal variation of CSF parameters. An aliquot of the CSF samples will be sent for local laboratory analysis (erythrocyte and leukocyte cell counts, protein, and glucose) while the remainder of the sample will be sent for central biomarker assessment. Any remaining CSF aliquots will be stored for the Research Biosample Repository for patients participating in RBR.
- 15 Premedication guidance is given in Section 4.4.2.
- 16 Study drug should be given as IV infusion at the same infusion rate as the last infusion in Part 2.
- 17 Skin biopsy must be collected pre-dose if the sample is collected on visits with study drug administration.
- 18 If participant discontinues or withdraws from the study treatment prematurely, they should complete all of the Part 3 Early Termination assessments and attend the Part 3 Follow-up visit normally done at the end of the study, 12 weeks after the last dose of study medication.
- 19 Should not be performed if already collected within 3 months of Part 3 early termination. If a Dat-SPECT scan is required for Part 3 early termination, TSH and T4 assessment should be performed prior to the scan.

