## **4.6 STUDY ASSESSMENTS**

### **4.6.1 Description of Study Assessments**

All examinations listed below will be performed according to the Schedule of Assessments (SoA) outlined in [Appendix 1](#), [Appendix 2](#) *and* [Appendix 3](#). A recommended sequence of assessments to be carried out at each visit is outlined in [Appendix 4](#).

Note that in those patients that start dopaminergic treatment during the course of the study, the majority of functional assessments (including MDS-UPDRS Part I + II + III) are to be performed prior to administration of dopaminergic treatment on that day. Only selected functional assessments such as MDS-UPDRS Parts III + IV will be performed at least 1 hour after dopaminergic treatment.

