## **Digital Biomarker In-Clinic Assessments**

*In Part 1 and Part 2*, participants are instructed to bring the smartphone and wearable to every clinic visit to check adherence and technical status of the devices. *In Part 1 and Part 2, participants will receive replacement device sets if they are defective. In Part 3, device sets may not be replaced if they are defective. In Part 3, participants are instructed to bring the sets to the visits with in-clinic digital biomarker assessments once a quarter.*

*In Part 1 and Part 2*, at selected clinic visits, participants will be asked to conduct the “Active Test” tasks and two additional in-clinic only assessments (selected items from the Berg Balance Scale and the Timed-Up and Go Test) under the supervision of a person trained on the digital biomarker approach. *In Part 3 participants will only perform the “Active Tests” at the specified in-clinic site visits.*

For participants who have started dopaminergic treatment (levodopa or dopamine agonist), the in-clinic assessments will be performed in a practically defined “Off” state

(i.e., no levodopa or dopamine agonist medication since the evening before). The in-clinic assessments will be repeated not earlier than one hour after receiving medication in clinic (“On” state).

The smartphone and wearable must be returned to the clinic in cases where the subject does not meet eligibility criteria, at the end of the study and upon early termination.

At the end of the study or at the time when the subject has completed the study, participants will be asked to complete a pen & paper satisfaction survey on how they experienced using the smartphone and wrist-based wearable during the study.

The full detailed digital biomarker is described in the ‘PD Digital Biomarker (Smartphone) Manual’.

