## Appendix 1 Schedule of Assessments (Part 1) (cont.)

- 10 MRI and DaT-SPECT scans should not be performed if already collected within 3 months of early termination. If a DaT-SPECT scan is required for early termination visit, TSH and T4 assessment must be performed prior to the scan.
- 11 Skin biopsy must be collected pre-dose if the sample is collected at visits with study drug administration.
- 12 At screening, Hoehn & Yahr staging will be assessed as part of the MDS-UPDRS Part III. MDS-UPDRS Part IV will be done for all participants on dopaminergic treatment (levodopa or dopamine agonist). For all participants that have started dopaminergic treatment, the MDS-UPDRS I-III, including Part IV and Digital Biomarker In-Clinic assessments will be assessed approximately 12 hours (e.g., overnight) after last dose of dopaminergic treatment. Only the MDS-UPDRS Part III and Digital Biomarker In-Clinic Assessments will then be repeated 1 hour after receiving dopaminergic treatment in the clinic.
- 13 The first Digital Biomarker In-Clinic Assessments should be done at least 7 days prior to Baseline. In Clinic Digital Biomarker Assessments include the Full Active Test, Short Berg Balance Test and Timed Up and Go.
- 14 Telephone interview on Day 2 and, for those subjects not participating in PK sampling, on Days 7 and 14 to assess for any clinically significant symptoms and/or new medication.
- 15 Abbreviated physical exam will include Head Ears Eyes Nose and Throat (HEENT), Heart & Lung exams and any complaints expressed by participant at visit.
- 16 MRIs should be performed with a time window of +/- 14 days from the study visit. DaT-SPECT should be performed within -14/-5 days if done prior to the visit clinic or within +14 days if done after the visit clinic. Refer to protocol Section 4.6.1.9 for procedure to follow in preparation of scans. In case participant takes dopaminergic treatment, MRI should be performed in a practically defined off state (no dopaminergic medication taken at the day of evaluation).
- 17 Fasting glucose will be analyzed at screening.
- 18 During screening, the Digital Biomarker Remote Monitoring should be started at least 7 days prior to Baseline. The PROs (patient reported outcome) are scheduled at regular intervals and administered on the digital biomarker smartphone. The PROs will typically be completed remotely since the scheduled days will often fall between clinic visit days.

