- 8 For consented participants only. The ideal collection time to perform Lumbar Puncture (LP) is between 48-72 hours after the Week 104 infusion and early termination. LP should be performed in the morning (between 8:00 and 12:00 hours) to minimize potential diurnal variation of CSF parameters. An aliquot of the CSF samples will be sent for local laboratory analysis (erythrocyte and leukocyte cell counts, protein, and glucose) while the remainder of the sample will be sent for central biomarker assessment. Any remaining CSF aliquots will be stored for the Research Biosample Repository for patients participating in RBR.
- 9 MRI and DaT-SPECT scans should not be performed if already collected within 3 months of early termination. If a DaT-SPECT scan is required for early termination visit, TSH and T4 assessment must be performed prior to the scan.
- 10 MDS-UPDRS Part IV will be done for all participants on dopaminergic treatment (levodopa or dopamine agonist). For all participants that have started dopaminergic treatment, the MDS-UPDRS Parts I- III, including Part IV and Digital Biomarker In-Clinic assessments, will be assessed approximately 12 hours (e.g., overnight) after last dose of dopaminergic treatment. Only the MDS-UPDRS Part III and Digital Biomarker In-Clinic assessments will then be repeated 1 hour after receiving dopaminergic treatment in the clinic.
- 11 Skin biopsy must be collected pre-dose if the sample is collected at visits with study drug administration.
- 12 In Clinic Digital Biomarker Assessments include the Full Active Test, Short Berg Balance Test, and Timed Up and Go.

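### The Part 3 schedule footnotes leave the in-clinic digital test out of the Off session and put MDS-UPDRS Part IV in both states, contradicting the rest of the protocol

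*Protocol*

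**What the plan says.** All the rules below concern participants who have started levodopa or a dopamine agonist.

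- **Parts 1 and 2.** In Appendix 1, footnote 12, Parts I to III, "including Part IV and Digital Biomarker In-Clinic assessments will be assessed approximately 12 hours (e.g., overnight) after last dose of dopaminergic treatment". The repeat is then limited: "Only the MDS-UPDRS Part III and Digital Biomarker In-Clinic Assessments will then be repeated 1 hour after receiving dopaminergic treatment in the clinic". Appendix 2, footnote 10, gives the same rule.
- **Part 3.** In Appendix 3 the Off sentence is shorter: "MDS-UPDRS Part III and Part IV will be assessed approximately 12 hours (e.g., overnight) after last dose of dopaminergic treatment". The post-dose sentence follows: "MDS-UPDRS Part III will then be repeated at least 1 hour after dopaminergic treatment along with MDS-UPDRS Part IV and Digital Biomarker assessments". The same two sentences stand in the footnotes for all five years. The digital in-clinic row has its own footnote (8 in Year 1, 6 in Years 2 to 5), which limits the content to the Full Active Test and gives no state.
- **Body text on the digital test.** Section 4.6.1.9 says that for treated participants "the in-clinic assessments will be performed in a practically defined" Off state, with a repeat no sooner than an hour after medication. Section 3.2.1 gives the same order and names Part 3 among the parts it covers.
- **Body text on Part IV.** Section 4.6.1.9 puts Part IV in the Off session and repeats only Part III. Section 4.6.1 differs: "Only selected functional assessments such as MDS-UPDRS Parts III + IV will be performed at least 1 hour after dopaminergic treatment".

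**The concern.** Section 3.3.4 lists in-clinic sensor data as an exploratory change from baseline to Week 52, Week 104 and Part 3 Week 260. At baseline nobody was on levodopa or an agonist. In Parts 1 and 2 a treated participant contributes an Off value and an On value. If Part 3 yields only a post-dose value, the series changes state between Week 104 and Part 3. Part of any apparent change would then be the response to symptomatic medication.

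Section 4.6.2.2 requires assessments to follow the schedule, so its footnotes are what a site will use on the day. A missing Off value cannot be restored by any later analysis plan.

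For Part IV the problem is inconsistency only. It is reported in participants who have started dopaminergic treatment, so there is no untreated baseline for it to shift from.

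**Working it through.** There is no stated figure to reproduce. The check is a comparison of the texts, a count of visits, and a bound on the consequence.

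**1. The rules side by side**

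| Source | In-clinic digital test | Part IV |
|---|---|---|
| Protocol 3.2.1 (names Part 3) | Off, then repeated On | Off |
| Protocol 4.6.1 | not addressed | after the dose |
| Protocol 4.6.1.9 | Off, then repeated On | Off; only Part III repeated |
| Appendix 1 footnote 12 | Off, then repeated On | Off only |
| Appendix 2 footnote 10 | Off, then repeated On | Off only |
| Appendix 3, five footnotes | named only after the dose | Off and after the dose |
| Appendix 4, dosing days | before the dose and again at least 1 hour after | before the dose |
| SAP 4.3.5 (Part 1) | not addressed | Off; only Part III repeated |

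On the digital test, Appendix 3 is the only source that omits the Off session. On Part IV there are three answers: Off only, after the dose, and both. The Part 3 Off sentence also drops Parts I and II, which Sections 4.6.1 and 4.6.1.9 place before the dose.

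**2. Visits exposed**

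Scheduled in-clinic digital visits in Appendix 3:

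- Year 1: Weeks 1, 12, 24, 36 and 52, which is 5.
- Years 2 to 5: 4 per year (for example Weeks 68, 80, 92 and 104 in Year 2), which is 4 × 4 = 16.
- Total: 5 + 16 = 21.

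The MDS-UPDRS is scheduled at the same 21 visits, so an Off session already takes place at each of them for treated participants.

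**3. What the omission could do to the mean**

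Let s be the share of participants on levodopa or an agonist, and d the On minus Off difference in the digital score. If only the On value is collected and analysed, the mean moves by s × d.

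- d is not in the documents. As an assumption for illustration, take 0.2 to 0.8 SD.
- s is not given for Part 3. Section 3.2.1 reports 14% to 50% starting within a year. Everyone treated is an upper bound.

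| s | d = 0.2 SD | d = 0.8 SD |
|---|---|---|
| 14% | 0.14 × 0.2 = 0.03 SD | 0.14 × 0.8 = 0.11 SD |
| 50% | 0.50 × 0.2 = 0.10 SD | 0.50 × 0.8 = 0.40 SD |
| 100% | 0.20 SD | 0.80 SD |

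If the Off test is done as Sections 3.2.1 and 4.6.1.9 require, and the Off value is the one analysed, the shift from this source is 0. The table shows how the result depends on the assumptions; it does not estimate a bias in this trial.

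**The case against.** A reader might infer that Part 3 deliberately moves the digital test to the On state, so that change from baseline drifts toward improvement by construction. The documents do not support that, for four reasons.

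- The footnote omits an Off digital test but does not forbid one. Part IV, named in the same post-dose phrase, was also done Off, so the digital test can be read as a repeat too.
- The body text still requires the Off test in Part 3. Section 3.2.1 names Part 3, and the Off/On paragraph in Section 4.6.1.9 directly follows a sentence about Part 3. Appendix 4, which was updated for Part 3 (its premedication line is limited to Parts 1 and 2), lists the digital test before and after the dopaminergic dose.
- No analysis uses the On value. The SAP covers Part 1 only. Its digital score analysis drops data after the start of symptomatic treatment, and its on-treatment sensitivity analysis of the primary endpoint uses Off data only (SAP 4.7.4).
- The argument does not reach Part IV, which is kept Off in Part 3, has no untreated baseline, and is already placed after the dose by Section 4.6.1.

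These points stand, and they rule out the stronger reading. They do not remove the contradiction. Section 4.6.2.2 makes the schedule binding. The status of Appendix 4 is itself unclear: the synopsis says its sequence must be followed, while Section 4.6.1 and the appendix title call it recommended. Its digital entries also still list the Berg items and the Timed Up and Go test, which Part 3 drops, so a site could take them as text for Parts 1 and 2. One post-dose digital session is a reasonable reading of the Part 3 schedule taken alone.

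**Conclusion.** Wrong as written: an internal contradiction. The five Part 3 footnotes conflict with Sections 3.2.1 and 4.6.1.9 and Appendices 1, 2 and 4 on the digital test. The state for Part IV is inconsistent across Section 4.6.1, Section 4.6.1.9, Appendices 1 and 2, and Appendix 3.

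The consequence is conditional. If sites follow the schedule alone, the Off digital value may be missing at up to 21 scheduled visits per treated participant. The change to Part 3 Week 260 would then not be comparable with Weeks 52 and 104. The size is unknown: it depends on a difference that the documents do not give and on a treated share that they do not give for Part 3. It is zero if the Off test is done and analysed.

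The digital measures and Part IV are exploratory, in an extension where everyone is on treatment. Part III Off ratings are retained in Part 3, and the Week 52 primary endpoint is untouched. The point is still worth correcting because a lost Off value is irrecoverable and the correction is nearly free.

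**What to change.** - **Footnotes.** In Appendix 3, Year 1 footnote 3 and Years 2 to 5 footnote 1, add Parts I and II and the in-clinic digital test to the Off sentence. Keep Part III and the digital test as the post-dose repeat. This brings the footnotes into line with Sections 3.2.1 and 4.6.1.9 and Appendix 4.
- **Do not paste in the Part 2 footnote whole.** That would delete the Hoehn & Yahr sentence and replace the minimum interval of one hour, which matches Section 4.6.1.9 and Appendix 4, with a flat one hour. Keep both.
- **Part IV.** Reconcile its state across Sections 3.2.1, 4.6.1 and 4.6.1.9 and Appendices 1 to 4, so that one rule applies throughout.
- **Part 3 SAP.** State that the Off digital value is used for change from baseline across parts. Record the state with each digital session, so that a lone post-dose value is not taken for an Off value.

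The cost is footnote wording, plus one short extra Active Test for treated participants inside an Off session that already exists. No additional withholding of medication is needed.
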